"Be yourself", educational intervention with chatbot to promote self-determined motivation and prevent adolescent pregnancy: pilot trial protocol

January 6, 2025

ABSTRACT

Introduction: Adolescent pregnancy and early initiation of sexual activity is a serious global public health problem, every year, around sixteen million adolescents between 15 and 19 years of age give birth, representing 11% of all births globally. **Objective:** To design a protocol of a pilot Randomized Controlled Trial to evaluate the preliminary efficacy of the "Be Yourself" intervention to increase self-determined motivation to prevent pregnancy in adolescents in secondary education. **Methods:** The protocol was developed based on the Protocol Items: ecommendations for Interventional Trials 2013 (SPIRIT2013) Statement, in the City of Monterrey, Nuevo León, Mexico in 2023. **Results:** The protocol outlined the design of the intervention, structured the content of the sessions using a logic model of intervention, and developed manuals for program facilitators and guides for participants. In addition, a website and a chatbot with Artificial Intelligence were developed, and the strategy for the application of the evaluation instruments was established.

Keywords: Self-determination; Teenage Pregnancy; Sexual behaviour; Prevention; Randomized controlled trial.

INTRODUCTION

Adolescent pregnancy continues to be a serious public health problem globally, affecting millions of young people every year. The World Health Organization (WHO) and the United Nations Population Fund (UNFPA) report that approximately sixteen million adolescents aged 15 to 19 give birth annually, accounting for 11% of all births. In addition, one in twenty adolescents contracts sexually transmitted infections (STIs) and 3.4 million children under 15 years of age live with Human Immunodeficiency Virus (HIV)^{1,2,3}. In Mexico, the rate of teenage pregnancies is the highest in the world, with more than 90% of new STIs in young women and a notable difference in the fertility rate between rural (2.8) and urban (2.01) areas, where 31.2% of young people under 18 years of age in rural areas are already mothers. compared to 18.3% in urban areas^{4,5,6}.

The literature reports that some reasons for risky sexual behaviors at this stage are ignorance of the use of contraceptive methods and how STIs are transmitted; lack of communication about sexual issues with parents, friends, and partners; lack of confidence in the proper use of condoms; and lack of sexual autonomy7,8. Different authors indicate that these reasons lead adolescents to some high-risk sexual behaviors, such as the early initiation of sexual relations and sexual relations without using a condom, so that at this stage the risk of unwanted pregnancies and STIs increases ^{1,9}.

Secondary sexual education remains essential to improving adolescent sexual health, as most adolescents attend school, and parents support its inclusion in the curriculum. However, many

adolescent pregnancy prevention programs, created decades ago, address only a limited range of risky behaviors. To increase effectiveness, technology has been integrated into these programs, although evaluations have not always demonstrated the specific impact of these technological components. In addition, it has been noted that programmes that rely solely on in-person education may not be in line with young people's current communication preferences^{10,11}.

Recent studies have evaluated technological adaptations in sexual and reproductive health programs, finding that access to websites, apps, and text messages may be promising, although more evaluation is required. Systematic reviews and meta-analyses have comprehensively analyzed interventions to reduce risky sexual behaviors in adolescents, highlighting the importance of psychological approaches based on theories such as Social Cognitive Theory, Planned Behavior Theory, Reasoned Action Theory, and Self-Determination Theory. While most reviews have focused on HIV and STI prevention, some have also addressed pregnancy prevention, often integrating both aspects into their approaches^{11,12}.

Global evidence indicates that psychological interventions can be effective in reducing risky sexual behaviors and preventing unwanted pregnancies. Adolescent sexual and reproductive health is therefore a national priority. In this context, Rodríguez's Self-Determination Model for Sexual Behavior for the Prevention of Pregnancy in Adolescence (MACSPEA)¹³ has proven to be useful in explaining and predicting pregnancy prevention behaviors, considering personal factors such as age, the beginning of sexual life and knowledge about prevention, as well as contextual factors such as sexual communication with parents, friends and partner. In addition, the model includes psychological factors such as intrinsic goals, satisfaction and frustration of basic psychological needs, and self-determined motivation^{14,15,16.}

For all the above, an educational intervention was developed based on the MACSPEA model, the six steps of Bartholomew's intervention mapping17 and the stages of the Transtheoretical Model of Change (MTTC) proposed by Prochaska and DiClemente18, in addition to a website that uses artificial intelligence (AI) through a chatbot as a delivery method. This intervention is aimed at adolescents aged 12 to 15 years, with the aim of evaluating the preliminary efficacy of the intervention called "Be yourself" to increase self-determined motivation and prevent pregnancies in secondary school adolescents.

MATERIAL AND METHODS

Studio Design

A randomized controlled pilot trial protocol has been developed following the guidelines of the Declaration SPIRIT¹⁹ 2013 and CONSORT²⁰ criteria, which provides a checklist to ensure quality and completeness in the development of protocols. This protocol corresponds to a randomized controlled pilot trial (RCT) with a pretest-posttest design, which will include a control group (CG) and an experimental group (EG) (Table 1).

Participants	Assigned Group	Measurement	Application	Measurement 1	Measurement 2
Teens	GE-1	Before	Intervention "Be yourself"	\rightarrow At the end	3 months
12 to 15 years	GC- 2	Before	Habitual	At the end	3 months

Table 1. Outline of the design of the Pilot RCT

Population Characteristics and Eligibility Criteria

The target population of the "Be Yourself" program are adolescents between 11 and 15 years old in secondary schools in Santa Catarina, Nuevo León. Eligibility criteria include being enrolled in a public school with access to a computer lab and internet, residing with your parents, and having become sexually active or not. The sample will be of 150 randomly selected participants. Participation will be assessed using a filter questionnaire, and adolescents will be required to register on the program's website throughout the intervention, with the option to withdraw at any time.

Sample size

To determine the sample size, the nQuery Advisor statistical package will be used. The aim is to have 150 participants, of which 75 will belong to the CG and 75 to the EG, applying a simple random probability sampling. The sample will be calculated with an error level of .05, a power of 90%, a moderate effect size of .3, considering a loss of 20%.

Design of the Intervention "Be yourself"

The "Be Yourself" educational intervention was designed to prevent sexual risk in high school adolescents through self-determined motivation. Based on MACSPEA, the model of stages of change and competency-based learning uses a website (https://www.s-t-mismo.com/) and a chatbot for monitoring and activities (Table 2). The intervention consists of three sessions that address the prevention of adolescent pregnancy and the strengthening of skills. It includes hands-on activities,

role-plays, and interactive sessions on contraceptive methods, effective communication, and informed decision-making. To do this, specialized human resources and specific materials are required for its execution. Manuals were designed for the intervention and training of the facilitator, and activity guides for adolescents^{21,14-18}.

		Thematic content	Time	Components of the intervention
		Pre-test assessment app	40 min	Access to the "Be Yourself" page
ų	1.	What is self-determined motivation?: Discovering our dreams	60 min	Personal factors
First Session	1.	My Body: Anatomy, Physiology, and Sexual Health.	60 min	 Age of onset of sexual life Pregnancy Prevention
	2.	Navigating relationships: preventing unplanned pregnancy in adolescents.	60 min	Knowledge
	3.	Exploring Goals and Values to Prevent Unintended Pregnancies	60 min	Contextual factors
Second Session	4.	Be yourself: stop, think and act; Introduction to Troubleshooting	60 min	1. Sexual communication with parents
	5.	Role-play: open dialogue about sexuality	60 min	 Sexual communication with friends Sexual communication with a partner
uo	6.	Navigating the Sea of Healthy Choices: Exploring Our Motivation	60 min	Psychological factors
Third Session	7.	My Space, My Decisions Exploring Our Needs	60 min	 Intrinsic and extrinsic motivation Satisfaction and frustration:
Thir	8.	Negotiating Healthy Choices: Preventing Pregnancy and STIs	60 min	autonomy, relationships and skills
Keep	9.	Building Self-Determined Motivation in Teens: Strengthening Session on Website and Chatbot	Continued individual	 Self-determined motivation, Behavioral Intent and Sexual Prevention Behavior
		Post-test assessment app	40 min	Access to the "Be Yourself" page
		Total, hours	10 hours 20	minutes more

Description of the control treatment

For the GC, two theoretical sessions are planned. In the first, an orientation on sexual health for adolescents will be offered through a one-hour PowerPoint presentation. Topics of anatomy, physiology, biological changes in adolescence and contraceptive methods will be addressed, highlighting their appropriate use and the prevention of teenage pregnancy. In the second session, also one hour, sexual health self-care skills will be developed, discussing the importance of self-care, self-respect, and informed decision-making. There will be a Q&A session to address concerns and reflect on how self-care contributes to a healthy and safe sex life.

Control measures

Randomization of participants

Participants will be thoroughly selected to represent the EG. Software will perform a simple, blinded randomization, assigning participants to control or experimental groups. Managers will be informed about the "Be Yourself" sessions, the dates and locations of which will be published on the website and communicated verbally. The sessions will be group, with individual activities on the website and through a chatbot.

Recruitment

Recruitment for the intervention will take place in February 2025, after the authorization of the educational authorities. Adolescents from the educational institution will be openly invited and their suitability will be evaluated according to inclusion criteria. Those selected will be recorded and assigned to control and experimental groups using an ID to ensure data integrity.

With informed consent, participants will access the website and the chatbot for information and registration. After accepting, they will answer filter questions and receive a detailed explanation of the process. Those who do not qualify will receive a transparent explanation.

On the website, participants will record their personal data for effective communication and reminders. They will be informed about the royalties of the program at the end of the project, motivating them to participate in all activities. The information will be stored securely for one year.

Measurements and data collection

Data collection for the study will include the use of a specifically designed Personal Data Card, which will collect information about the sexuality, marital status, and education of the participants. A variety of scales will be used to measure aspects related to adolescent sexual health and behavior. The Sexual and Reproductive Health Knowledge Scale, Cronbach's alpha between .77 and .81²¹, will assess knowledge in these areas, while the Sexual Issues Communication Instrument, Cronbach's alpha from .89 to .95, will analyze sexual communication between parents, friends, and partners²². The Aspirations Index, alpha greater than .78 and .94, will measure life goals, and the Basic Psychological Needs Satisfaction and Frustration Scale will have alphas of .90 and .86²³.

[figure not shown]
The Behavior Regulation Questionnaire, adapted to the Mexican context, will assess behavior regulation to prevent pregnancy, with alphas between .66 and .93²⁴. Likewise, the Sexual Activity Intention Scale and the Sexual Activity Scale will assess sexual intentions and behaviors, respectively, with alphas from .83 to .88 and .74 to .86²⁵. The Sexual and Reproductive Health

[figure not shown]
Practices Scale, which examines pregnancy prevention behavior, with alphas of .92, .77, .81 and .87 in its different adaptations²⁶.

The "Scale for the Assessment of Change on Sexual Behavior in Adolescents"27 will be adapted and validated, ensuring its reliability. To assess the acceptability and feasibility of the "Be Yourself" intervention, aspects such as participant satisfaction, meeting expectations, and facilitator quality will be analyzed, along with participant recruitment, screening, randomization, and retention procedures.

Participant Retention Plan and Follow-Up

The retention plan for the "Be yourself" intervention includes the delivery of T-shirts and caps with the logo of the program at the end, weekly sessions to avoid information saturation and a three-month follow-up. Data collection will be done through the website using digital tools to assess the effectiveness and acceptability of the program. The fidelity of the intervention will be ensured by training the principal investigator in self-determination theory and developing supporting manuals and guides. Figure 1 presents diagram CONSORT²⁰, which details the eligibility criteria, intervention, and evaluation of sessions before, after, and during follow-up at three months.

Ethical considerations

This study complies with the ethical regulations of the Regulations of the General Health Law, ensuring respect for the dignity and rights of the participants. The protocol has been approved by the Ethics and Research Committee of the Faculty of Nursing of the Autonomous University of Nuevo León, with registration number FAEN-D-2021. Informed consent will be obtained from the parents and assent from the adolescents. Participation will be explained in detail to parents and teens, including risks and benefits. The research will be suspended if there is a risk to the health of the participants or if they wish to withdraw²⁸.

Data analysis plan

The research will use statistical software SPSS version 26.0 for data processing. The analysis will begin with the Kolmogorov-Smirnov test to evaluate the distribution of the data and determine the suitability of applying parametric or nonparametric tests. The statistical analysis will include a descriptive level, using percentages, means, and standard deviation, to assess feasibility and acceptability. For hypotheses, inferential tests such as paired sample t-test, ANOVA, and Mann-Whitney U will be used to examine knowledge about pregnancy prevention, sexual communication, motivation, satisfaction of psychological needs, sexual intention, pregnancy prevention behavior, and stages of change in sexual behavior²⁹.

Table 3 describes the objectives and hypotheses proposed in this study, both descriptive and inferential statistics will be used

Objective	Analysis	Statistical
1 Examining feasibility	Descriptive	Measures of frequency, central tendency, and dispersion: percentages, means, ranges, Standard Deviation, confidence intervals, recruitment and retention rates.
2 Analyze acceptability	Descriptive	Percentages, means, ranges, Standard Deviation, confidence intervals, recruitment and retention rates
Hypothesis	Analysis	Statistical
 3 Hypothesized results: H 1. Knowledge about Pregnancy Prevention H 2. Sexual Communication Parent, Friends & Partner. H 3. Intrinsic and extrinsic motivation H 4. Satisfactory and Frustration of NPBs (autonomy, relationship and competencies) H 5. Self-Determined Motivation H 6. Intention in Sexual Activity H 7. Pregnancy Prevention Sexual Behavior H 8. Stages of Change for Sexual Behavior 	Inferential	t-test of paired or ANOVA samples Test de Friedman Test de Wilcoxon U de Mann-Whitney

Table 3. Statistical analysis by objective and/or hypothesis

EXPECTED RESULTS

The protocol of the "Be Yourself" intervention includes the structural design of the sessions, the development of two facilitator manuals and a participant workbook, and the creation of a web page with a chatbot based on OpenAI's GPT. The intervention is expected to increase adolescents' self-determination to abstain from sexual activity, improve their positive attitude toward sexuality, and expand their knowledge about pregnancy prevention. In addition, a greater adoption of preventive behaviors is anticipated compared to those who do not participate, which would suggest a positive impact on sexual decision-making.

FINANCING

This project did not receive any funding **DECLARATION OF CONFLICTS OF INTEREST** The author declares that they have no conflict of interest

REFERENCES

- World Health Organization (WHO)/PAHO. Syndromic management of sexually transmitted infections. 2022. ISBN 9789243593401. [Accessed July 19, 2024]. Available in: https://www.paho.org/es/temas/infecciones-transmision-sexual/manejo-sindromicoinfecciones-transmision-sexual
 - UNFPA. Systematization of scientific evidence on Comprehensive Sexuality Education. Updated version with new evidence about out-of-school HIE. UNFPA Regional Office for Latin America and the Caribbean, Panama. 2020. [Accessed July 19, 2024]. Available in: https://www.aprofaeduca.cl/wp-content/uploads/2021/08/Sistematizacio%CC%81n-deevidencias-cienti%CC%81ficas-sobre-la-Educacio%CC%81n-Integral-de-la-Sexualidad.pdf

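### The 150 assumes independent adolescents, but sessions are given in groups: with positive within-group correlation the named between-arm tests exceed .05, and a valid adjusted test has less than 90% power

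*Protocol*

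**What the plan says.** The protocol describes a "randomized controlled pilot trial (RCT) with a pretest-posttest design". Under Sample size it aims for 150 participants, 75 per arm, "calculated with an error level of .05, a power of 90%, a moderate effect size of .3, considering a loss of 20" per cent. It does not say which effect measure the .3 refers to.

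Under Randomization of participants, allocation is individual: "Software will perform a simple, blinded randomization, assigning participants to control or experimental groups". The same paragraph then says of the Be Yourself sessions: "The sessions will be group, with individual activities on the website and through a chatbot". The section on the design of the intervention lists "role-plays, and interactive sessions on contraceptive methods, effective communication, and informed decision-making". The control arm has two one-hour sessions, and of the second it is said: "There will be a Q&A session to address concerns and reflect on how self-care contributes to a healthy and safe sex life". That suggests a group format for control but does not state it.

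Under Data analysis plan, "inferential tests such as paired sample t-test, ANOVA, and Mann-Whitney U will be used"; Table 3 adds the Friedman and Wilcoxon tests. Of all these, only ANOVA and Mann-Whitney can compare the two arms.

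The number and size of the session groups and an ICC appear nowhere.

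**The concern.** Adolescents who sit through the same role-plays and discussions, with the same peers, may end up with more similar scores than adolescents in different groups. Randomising individuals does not prevent this, because the correlation arises after allocation, through delivery. ANOVA and Mann-Whitney count each adolescent as a separate piece of information. With positive correlation they understate the uncertainty of the arm difference, and a chance difference between session groups can pass for an effect of Be Yourself. The sample size has no room for this, since loss is the only inflation.

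One part cannot be mended afterwards. If each arm were taught as a single group, no analysis could separate the effect of the programme from the effect of that group. Likewise, if session membership is not captured at delivery, the ICC cannot be estimated for the next trial, which is one of the useful products of a pilot.

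**Working it through.** **Step 1: the plan's own figure.** Inputs from Sample size: error level .05 (two-sided assumed), power 90%, effect .3, loss 20%, 75 per arm. Analysed per arm: 75 × 0.8 = 60.

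- Read as Cohen's f = .3, the difference between two arms is 2 × .3 = 0.6 SD. The noncentrality is 0.6 × √(60/2) = 3.286, and with 118 degrees of freedom (df) power is 90.3%. With 59 per arm it is 89.8%. So 60 per arm are needed, and 60/0.8 = 75 per arm, 150 in all. This matches exactly.
- Read as a paired standardised change of .3, 119 pairs give 90.1%, and 119/0.8 = 148.75, so 149. This also treats participants as independent, but it does not compare two arms.
- Read as Cohen's d = .3, 60 per arm gives only 37% power even without grouping, so this reading does not lead to 150.

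**Step 2: assumptions for grouping.** None of these is in the protocol: five session groups of 15 enrolled per arm (5 × 15 = 75); loss spread evenly, leaving m = 12 analysed per group (5 × 12 = 60); ICC .01, .02 or .05; effect 0.6 SD.

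The design effect is DE = 1 + (m − 1) × ICC = 1 + 11 × ICC, which gives 1.11, 1.22 and 1.55.

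**Step 3: both arms grouped.**

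- False-positive rate of the ordinary test: 2 × [1 − Φ(1.96/√DE)].
- Its apparent power: about Φ((3.286 − 1.98)/√DE).
- Power of a test that allows for the correlation: noncentrality 3.286/√DE, with 118 df if the small number of groups is ignored, or 2 × (5 − 1) = 8 df for a t-test on group means.

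| ICC | DE | Ordinary test, false positives | Ordinary test, apparent power | Adjusted power, 118 df | Adjusted power, 8 df |
|---|---|---|---|---|---|
| 0 | 1 | 5.0% | 90% | 90% | 82% |
| .01 | 1.11 | 6.3% | 89% | 87% | 78% |
| .02 | 1.22 | 7.6% | 88% | 84% | 74% |
| .05 | 1.55 | 11.5% | 85% | 75% | 64% |

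A simulation of the ordinary t-test (40,000 trials per setting) gave false positives of 6.3%, 7.7% and 11.4%, and power of 89%, 88% and 85%.

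**Step 4: only the experimental arm grouped.** The arm-mean variances are DE/60 and 1/60, so the average design effect is (DE + 1)/2 = 1.055, 1.11 and 1.275. Satterthwaite df = (v₁ + v₀)² / (v₁²/4 + v₀²/59) = 13.7, 12.7 and 10.5 (15.0 at ICC 0).

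| ICC | Ordinary test, false positives | Adjusted power, 118 df | Adjusted power, Satterthwaite df |
|---|---|---|---|
| 0 | 5.0% | 90% | 87% |
| .01 | 5.6% | 89% | 84% |
| .02 | 6.3% | 87% | 82% |
| .05 | 8.3% | 82% | 75% |

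**The case against.** Every magnitude above is assumed. At an ICC of 0 the stated .05 and 90% hold, and with small groups and a small ICC the departure is slight: for groups of 10 and an ICC of .01, the false-positive rate is .061. The effect of 0.6 SD itself rests on an unstated reading of .3. All of this stands. It limits the size of the problem but not its direction, since any positive ICC with more than one adolescent per group makes DE larger than 1.

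A reader might infer that power with the named tests collapses. It does not. The ordinary test keeps about 89% to 85% apparent power in the case with both arms grouped, and it does so by rejecting too often. The lower power figures belong to adjusted tests that the protocol does not name. Part of the lowest column is not due to correlation at all: the group-means test on 8 df has 82% power at ICC 0.

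A reader might also infer that session membership will not be recorded, because Recruitment says only: "Those selected will be recorded and assigned to control and experimental groups using an ID to ensure data integrity". The protocol does not say whether membership is recorded. Participants register on the website throughout, and session dates and locations are published there, so the information may exist.

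The model is properly a matter for an analysis plan, the list of tests is introduced as examples, and this is a pilot. But the protocol itself claims .05 and 90%, sets out to assess preliminary efficacy, and tests its hypotheses inferentially. How many groups are run and who sat in which must be settled when sessions are delivered; a later plan cannot restore that.

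**Conclusion.** The point holds in conditional form. The 150 is a calculation for independent participants with no slack, whereas delivery is in groups and the between-arm tests named ignore groups. If scores within session groups are positively correlated, the main consequence with those tests is a false-positive rate above .05. With five groups of 15 enrolled per arm and an ICC of .01 to .05, it is about 6% to 12% if both arms are grouped and about 6% to 8% if only the experimental arm is. A test that allows for the grouping has less than the stated 90% power: 87% to 75% (both arms) or 89% to 82% (one arm) before, and 78% to 64% or 84% to 75% after, allowing for the small number of groups. The protocol does not show that the correlation is present or how large it is. This should be fixed before sessions start, but it does not invalidate the trial.

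**What to change.** Keep N = 150 and make these changes:

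- **Delivery and data.** Plan more than one session group per arm, state their number and size, and record a session-group ID for every participant at delivery.
- **Between-arm analysis.** Include session group as a random effect, in one or both arms as delivered, with small-sample degrees of freedom and baseline adjustment. Report the ICC. Model detail can go in the statistical analysis plan.
- **Sample-size paragraph.** Name the effect metric and, if the Cohen's f reading is the one meant and the assumed grouping is adopted, restate: *60 analysed per arm gives 90% power for a 0.6 SD difference only if participants are independent; with 5 session groups of 15 enrolled (12 analysed) in each arm and an assumed ICC of .01 to .05, power without baseline adjustment is about 87% to 75%, or 78% to 64% allowing for the small number of groups.* If the actual groups differ, recompute.

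The cost is one data field, a stated session schedule, a different between-arm model and a reworded paragraph, with no extra participants. Intervals will be wider and the stated power lower. Baseline adjustment recovers part of it. With an assumed pre-post correlation of .5 and the group variance unreduced, the variance factor is 0.75 + 11 × ICC = 0.86, 0.97 and 1.30. Power with both arms grouped is then 94%, 91% and 82% (117 df), or 87%, 83% and 71% on 8 df.

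### The randomisation section opens by selecting participants for the experimental group, which contradicts the software randomisation in its next sentence

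*Protocol*

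**What the plan says.** The protocol describes how pupils enter the study and reach an arm in several places.

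- **Studio Design:** "This protocol corresponds to a randomized controlled pilot trial (RCT) with a pretest-posttest design", with a control group (CG) and an experimental group (EG).
- **Control measures, Randomization of participants, first sentence:** "Participants will be thoroughly selected to represent the EG".
- **Same section, second sentence:** "Software will perform a simple, blinded randomization, assigning participants to control or experimental groups".
- **Recruitment:** "Adolescents from the educational institution will be openly invited and their suitability will be evaluated according to inclusion criteria", followed by "Those selected will be recorded and assigned to control and experimental groups using an ID to ensure data integrity".
- **Sample size:** "The aim is to have 150 participants, of which 75 will belong to the CG and 75 to the EG".

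The protocol does not say what representing the EG means, who would do the selecting, or on what criterion.

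**The concern.** The first sentence of the allocation section names one arm only. In its plain meaning, particular pupils are picked for the EG and the CG is whoever remains. The second sentence says software decides, at random, who goes to which arm. Both cannot be the operating rule.

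Random allocation is what makes the two groups comparable before the intervention. The trial aims at preliminary efficacy on self-determined motivation, an outcome on which pupils picked as suitable for the programme could easily differ from the rest. Measurements and data collection also lists randomisation among the procedures whose feasibility will be examined, so the procedure under examination needs a single, unambiguous description. This is protocol content that is stated and then contradicted, not a detail that could be left to an analysis plan.

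**Working it through.** The protocol states no figure on this point, so the check is mainly a comparison of texts.

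**1. The two sentences side by side.** Sentence one: the action is selection, the target is the EG, and the CG is not mentioned. Sentence two: the action is randomisation by software, and the target is either group. If membership of the EG is fixed by selection, the software has nothing left to decide. If the software decides, nobody can have been selected for the EG. Read literally, the sentences exclude each other.

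**2. Does other text explain the first sentence?** Studio Design calls the trial randomised. Recruitment puts selection before assignment, and the assignment is to both groups, which fits selection meaning eligibility screening. No section says that this is what the EG sentence means. The word is also used in another sense under Population Characteristics and Eligibility Criteria: "The sample will be of 150 randomly selected participants". That concerns sampling, not allocation, and is a separate matter, but it shows that the word has no fixed meaning in this protocol.

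**3. Is the ID wording a further contradiction?** No. The Recruitment sentence gives data integrity as the purpose of the ID. That is record-keeping, and it is compatible with concealed random assignment of coded participants.

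**4. Could the listed analyses undo selection, if it happened?** Data analysis plan and Table 3 name the paired t-test, ANOVA, Friedman, Wilcoxon and Mann-Whitney U. Write τ for the true effect, b for the baseline gap (EG minus CG) created by selection, and g for the gap in how much the two groups would have changed anyway.

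- Post-test comparison between arms: expected difference = τ + b + g.
- Comparison of pre-post change between arms: expected difference = (τ + b + g) − b = τ + g.

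Using the pre-test removes a constant baseline gap b. It does not remove g, for example if pupils were picked because they seemed ready to change. Under random assignment both b and g are zero in expectation.

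**5. Can the bias be sized against the plan's effect size of .3?** No. The documents contain nothing from which b or g could be estimated, and the metric of .3 is not stated. The sample size shows how much the metric matters. Take two-sided α = .05 (an assumption, since sidedness is not given), 90% power, and (1.960 + 1.282)² ≈ 10.51.

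| Reading of .3 | n before loss | Total after 20% loss |
|---|---|---|
| Cohen's f, so d = 0.6 for two groups | 2 × 10.51 / 0.36 = 58.4, so 59 per arm, 118 in all | 118 / 0.8 = 147.5, so 148 |
| Cohen's d = 0.3 | 2 × 10.51 / 0.09 = 233.5, so 234 per arm, 468 in all | 468 / 0.8 = 585 |
| Standardised paired change of 0.3 | 10.51 / 0.09 = 116.7, so 117 in all | 117 / 0.8 = 146.25, so 147 |

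With the exact t-test the first reading needs 60 per arm, and 60 / 0.8 = 75 per arm, which is the plan's figure. A between-group difference of 0.3 SD does not lead to 150.

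**The case against.** The strongest reply is that the allocation mechanism is clear everywhere except in this one sentence. The very next sentence assigns by software, the design is declared randomised, and Recruitment selects first and then assigns to both groups. No person, step or criterion for choosing pupils into the EG appears anywhere. The text also reads as a translation, so the sentence may simply mean that the study sample is chosen with care. This stands as an account of the probable intent, and it limits the point to a contradiction. It does not make the sentence harmless, because staff follow what the allocation section says.

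Three stronger readings are tempting, and the documents do not support them.

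- **The EG will be hand-picked.** A reader might infer this from the sentence alone. The surrounding text points to random assignment instead.
- **Pupils are allocated by identifier.** A reader might infer this from the ID wording in Recruitment. The sentence gives a data-integrity purpose, and no rule links an ID to an arm.
- **Selection could produce a false difference as large as the target effect.** This needs an assumed shift with no source in the protocol, a reading of .3 as a difference in SD units that does not fit the stated 150, and an analysis that ignores the pre-test. Nor is it right that the listed tests are powerless: a pre-post comparison between arms would remove a constant baseline gap.

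**Conclusion.** The point holds as a contradiction within the section that defines allocation. The first sentence, read literally, is incompatible with the second and with the declared randomised design, and no other text resolves it. The harm is conditional: it arises only if someone applies the sentence as written, in which case the arms would differ through selection and the listed tests could correct this only in part. Its size cannot be stated from the documents. The conclusion rests on the plain meaning of the two sentences and on no numerical assumption. Because the intent is probably sound and the repair is easy, it should be corrected before any pupil is allocated, but it is not evidence that the trial is non-randomised.

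**What to change.** Delete the sentence about selecting participants for the EG and state one rule in its place:

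- Eligible pupils with parental consent and their own assent are enrolled and each given a study ID.
- Only after that does the software randomly assign each ID to CG or EG.
- The assignment stays concealed until enrolment is complete, and no staff member chooses an arm.

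The ID sentence in Recruitment is not an error and can stay; a cross-reference from it to this rule would help the reader. The cost is one deleted sentence and a short replacement. It uses the software randomisation that the protocol already names, and the sample size, measurements and listed tests do not change.
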